2.3.3. Overall Benefit: Risk Conclusion

Taking into account the efficacy and safety data collected up to date, the benefit-risk assessment supports further testing of efgartigimod PH20 SC in participants with pemphigus.

3. OBJECTIVES AND ENDPOINTS

Objectives	Endpoints				
Primary					
• To assess the safety of treatment, extended treatment, and retreatment with efgartigimod PH20 SC in participants with PV or PF	• Incidence and severity of treatment-emergent adverse events (TEAEs), adverse events of special interest (AESIs), and serious adverse events (SAEs) by system organ class (SOC) and preferred term (PT)				
	• Vital sign measurements, physical examinations, electrocardiograms (ECGs), and clinical laboratory safety evaluations				
Secondary					
• To evaluate the efficacy of efgartigimod PH20 SC treatment in PV and PF	Proportion of PV participants who achieve CRmin				
	• Proportion of PV and PF participants who achieve CRmin				
	• Time to DC				
	• Time to CR				
	• Time to CRmin				
	• Time to CRoff				
	• Time to flare				
	• Rate of treatment failure				
	• Rate of flare				
	• Cumulative prednisone dose over the trial				
	• Pemphigus Disease Area Index (PDAI) at each visit				
• To assess the health impact of glucocorticoid (GC) use in participants with PV or PF	• Composite Glucocorticoid Toxicity Index (C-GTI) comprising the Aggregate Improvement Score (AIS) and the Cumulative Worsening Score (CWS)				
• To evaluate the effects of efgartigimod PH20 SC on quality of life (QoL) in participants	• EuroQol 5-Dimension 5-Level (EQ-5D-5L) score				
with PV or PF	• Autoimmune Bullous Disease Quality of Life (ABQOL) score				
• To evaluate the pharmacokinetics (PK) of efgartigimod PH20 SC in participants with PV or PF	• Efgartigimod serum concentrations				
• To evaluate the PD of efgartigimod PH20 SC in participants with PV or PF	• Total IgG and subtype (IgG1, IgG2, IgG3, IgG4) serum levels				
	• Anti-Dsg-1 and -3 autoantibodies serum levels				

Objectives	Endpoints			
• To evaluate the immunogenicity of efgartigimod in participants with PV or PF	• Incidence and prevalence of antidrug antibodies (ADA) against efgartigimod (serum levels)			
• To explore feasibility of self-administration of efgartigimod PH20 SC	• Percentage of participants who performed self-administration			
	• Percentage of caregivers who administered the injection to the participant			
	• Number of visits needed for the participant or caregiver to be competent to start administering efgartigimod PH20 SC			
	• Frequency of self- or caregiver-supported administration at home			
Exploratory				
• To evaluate the disease-specific genetic background and effects of efgartigimod PH20 SC on the serological and immunological profiles of participants with PV or PF	 Anti-Dsg-1 and -3 autoantibody subclasses and autoantibody reactivity to Dsg domains and other antigens Lymphocyte dynamic changes 			
• To evaluate the immunogenicity of rHuPH20 in participants with PV or PF	• Immunogenicity to rHuPH20 (plasma levels)			

- flare between DC and achieving CRmin that is not controlled by 2 dose levels of OCS above the dose at which the flare is observed and that is at least 0.3 mg/kg/day (Table 4)

In the absence of DC, participants will receive prednisone at the starting dose of 1.5 mg/kg/day. In case of uncontrolled flare before CRmin, participants will receive, as starting dose, the last dose from ARGX-113-1904. In case of flare after CRmin, participants will receive a prednisone dose in line with the severity of the flare, with the recommendation of a minimum of 0.3 mg/kg/day when the flare is of mild severity (PDAI activity score <15) and of 0.5 mg/kg/day when the flare is moderate to severe (PDAI activity score \geq 15). Dosing of efgartigimod PH20 SC will be done during on-site visits or home visits according to Table 2.

5. Participants who developed a prednisone-related SAE may prematurely roll over into ARGX-113-1905 and may be treated with efgartigimod PH20 SC through on-site or home visits according to the clinical statuses as described above. Concomitant prednisone will be considered to fit the clinical statuses as described above as far as compatible with the nature and severity of the SAE, with a lower dose to no concomitant prednisone being considered otherwise.

Participants or their caregivers (a person of legal age that the participant proposes to perform the administrations) may self-administer efgartigimod PH20 SC after they have successfully completed self-administration training (in ARGX-113-1904 with at least 1 refresher training in OLE trial ARGX-113-1905, or during ARGX-113-1905). All participants and/or their caregivers will receive a home guide for transport, storage, preparation, and administration of the IMP.

At any postbaseline visit before DC is achieved, the prednisone dose will be adjusted by incrementing dosage according to clinical judgment, with the recommendation to increase by 1 or more steps (Table 4) in case of disease progression or insufficient clinical change. To facilitate common judgments among investigators, recommendations for assessment of disease progression and insufficient clinical change are:

- Disease progression: increase of at least 5 in PDAI activity score compared to baseline score, observed at any postbaseline visit before DC
- Insufficient clinical change: the absence of DC after 3 to 4 weeks of the participant being treated at the starting baseline prednisone dose or after 3 to 4 weeks of any new incremented dose of prednisone

The recommendations of the prednisone dose escalation are:

- Stepwise escalation of daily prednisone dose by 1 or more steps according to clinical judgment in case of disease progression
- Adjustment by incrementing dosage by 1 step in case of insufficient clinical change
- Possible further escalation from the previous step by 1 or more steps, according to clinical judgment and under the same recommendation as above
- Maximum escalation to 1.5 mg/kg qd for 3 weeks

If DC is not attained after a minimum of 3 weeks of the participant receiving oral prednisone 1.5 mg/kg qd, then the participant will be considered a treatment failure and will be withdrawn from the trial.

For participants who achieve DC at the starting dose of 0.5 mg/kg qd or lower, the prednisone dose will be maintained at that starting dose qd until CR and 2 weeks thereafter, or EoC and 4 weeks thereafter, after which tapering will be initiated. For participants achieving DC with an escalated prednisone dose (ie, >0.5 mg/kg qd), that dose will be maintained until 2 weeks after achieving DC and then will be tapered (Table 4) in increments of 0.25 mg/kg every 2 weeks until the starting dose is achieved. This starting dose will be maintained until a sustained CR is achieved for 2 weeks, after which further tapering will be initiated, or prednisone tapering below 0.5 mg/kg qd may be initiated in case of sustained EoC for 4 weeks. Further tapering will be performed thereafter, as long as CR or EoC are sustained. Each new tapered prednisone dose until 20 mg/day must be maintained for 2 weeks. Then, the prednisone dose is further tapered by 2.5 mg/day per week. When 10 mg/day is reached, this dose level will be maintained for at least 8 weeks until CRmin is achieved. The prednisone dose can then be further tapered to reach CRoff according to the clinical judgment of the investigator.

At visits when at least 1 new lesion is observed or established lesions remain extensive without being defined as a flare (ie, the appearance of 3 or more new lesions in a 4-week period that do not heal spontaneously within 1 week, or by the extension of established lesions in a participant who had achieved DC), the prednisone dose will be maintained or may be increased, according to clinical judgment. If the lesion resolves, tapering of the prednisone dose will be pursued as planned.

In case of flare in the period between DC and CRmin, the prednisone dose will be increased to achieve DC again. If the flare occurs after CR and IMP was administered at home by a nurse, the participant will resume weekly on-site visits until he/she achieves CR again. Participants who are not controlled by a dose of OCS that is 2 dose levels above the dose at which the flare is observed and that is at least 0.3 mg/kg/day (Table 4) will be managed according to clinical judgment ie, either receive a further increased prednisone dose or be withdrawn from the trial. Withdrawal of participants with a flare before CRmin will be defined as treatment failure.

In case of flare after having achieved CRmin (ie, while being off efgartigimod treatment), participants will be immediately treated/retreated with a new cycle of efgartigimod PH20 SC. The first day of new efgartigimod treatment will define a new baseline for assessments of outcomes (DC, CR, etc) and prednisone escalation or tapering schedule.

In the new treatment cycle, participants will be administered efgartigimod PH20 SC at a weekly dose of \square mg for the first \square , followed by weekly SC administrations of 1000 mg until CRmin. Oral prednisone will be administered at a dose chosen according to clinical judgment, with the recommendation of 0.3 mg/kg qd in the case of mild flare (PDAI activity score <15) and 0.5 mg/kg qd in the case of moderate to severe flare (PDAI activity score \geq 15). The treatment goal of a new treatment cycle is to first achieve DC again and therefore these participants will be treated accordingly (Table 2).

A new treatment cycle of efgartigimod PH20 SC can be initiated in eligible participants until week 44. In participants requiring a new treatment cycle of efgartigimod PH20 SC between weeks 45 and 49, the initiation will be optional and based on clinical judgment and participant consent. A new efgartigimod treatment cycle will not be permitted after week 49 to ensure a minimum of 4 weeks of efgartigimod treatment/cycle.

Except for oral prednisone, no other systemic therapies (eg, immunosuppressants, IVIg, immunoadsorption, anti-CD20 biologics) will be permitted during the trial.

Trial procedures will be performed per the SoA as detailed in Section 1.3 and Section 10.11.

4.2. Scientific Rationale for Trial Design

Pemphigus is a chronic disease and patients under treatment have intermittent episodes of clinical remission and flare. The mainstays of therapy in PV are systemic corticosteroids and rituximab. Corticosteroids rapidly affect PV symptoms (3–4 weeks), but must be administered at high daily doses (eg, oral prednisone 1–1.5 mg/kg) to attain effectiveness. At such high doses, the well-known cumulative toxicities common to corticosteroid treatment occur frequently, and using short courses at the lowest possible dosage by tapering gradually while keeping the disease in remission is the therapeutic goal. Recently, rituximab has been approved in adults with moderate to severe PV. When administered as adjunctive treatment to a short course of prednisone, rituximab, while having a relatively late onset of action, was shown to induce a higher rate of remission after 1 or 2 years, and a longer duration of remission than prednisone alone; however, administration of rituximab IV frequently results in IRRs and AEs, which may be of late onset.

An innovative drug is needed for the treatment of PV and PF that has a fast onset of action (eg, early DC, CR within weeks), a strong prednisone sparing effect, and a favorable safety profile.

Antecedent trial ARGX-113-1904 intends to demonstrate that efgartigimod PH20 SC with an add-on therapy of low doses of oral prednisone is a possible treatment modality for PV and PF which leads to early disease remission at minimal prednisone dose. The trial has a treatment phase of up to 30 weeks, and provides a tailored dose regimen for participants by stopping IMP administration upon achieving CRmin (defined as the absence of new lesions and complete healing of established lesions while the participant is receiving minimal prednisone therapy of $\leq 10 \text{ mg/day}$ for at least 2 months [8 weeks]). Note: when 10 mg/day is reached in ARGX-113-1904 or ARGX-113-1905, this dose level must be maintained for 8 weeks until CRmin has been achieved.

Study ARGX-113-1905 provides efgartigimod PH20 SC extended and retreatment options for participants who were randomized to the efgartigimod PH20 SC treatment arm in ARGX-113-1904, and provides first treatment and retreatment options for participants who were randomized to the placebo treatment arm in study ARGX-113-1904.

At blinded rollover from ARGX-113-1904 into ARGX-113-1905 participants may be in different clinical stages. Participants may have achieved CRmin, participants may have achieved CR without meeting the minimal therapy criterion, participants may have achieved DC or EoC (the time at which no new lesions have developed for a minimum of 2 weeks and approximately 80% of lesions have healed) without having achieved CR, participants may have had treatment failure or a flare after having achieved CRmin.

ARGX-113-1905 evaluates the ability to (further) taper prednisone therapy and achieve CRoff, the ability to achieve CR and CRmin for participants who had not yet achieved CRmin, and the

ability to treat flare; and assesses patient outcome measures and the safety, PD, PK, and immunogenicity of efgartigimod PH20 SC over the duration of the trial. Duration of CR, time to CRoff and the effects of retreatment by the study drug will be specifically evaluated during the trial.

4.3. Justification for Dose

SC administration is highly preferred over an IV formulation for patients with pemphigus, given the expected need for weekly administration over prolonged durations. Therefore, efgartigimod with rHuPH20 will be administered SC weekly until CRmin; retreatment may be initiated in case of flare after having achieved CRmin. To achieve a fast PD effect and clinical response a dose of mg will be administered in the first **manual**, followed by weekly doses of 1000 mg to maintain the PD effect and related clinical response.

Active pemphigus is seen by most clinicians as a disease that requires urgent control. Signs of activity include the extension of the lesions (eg, mucosal lesions becoming mucocutaneous in PV) and the sharp increase in anti-Dsg serum levels. In such circumstances, respiratory infections related to lesions of the mouth or throat as well as skin infections are frequent. Infections are today the first cause of mortality in pemphigus. The exposure to non-targeted immunosuppressive therapies such as high doses of corticosteroids and immunosuppressants is a co-morbidity factor.

ARGX-113-1701 showed that efgartigimod treatment resulted in a rapid DC with or without associated prednisone, as well as complete remission associated with low to intermediate prednisone doses (0.25 to 0.5 mg/kg per day).

In view of the severity of the disease a fast onset of action is desirable. Therefore, the proposed dose regimen for this trial starts with a dose that achieves close to maximal IgG reduction within 2 weeks with a goal of a reduction in time to a clinically relevant improvement. Subsequently, a lower weekly dose is expected to maintain improvement in this population.

As pathogenic IgGs are key to the pathophysiology of pemphigus, the selected doses and dose regimen target a nearly maximal PD effect (ie, reduction of pathogenic IgGs). Considering the chronic nature of pemphigus, where patients are typically treated chronically for years with corticosteroids or immunosuppressants, the dosing regimen of a weekly regimen reflects the need for chronic treatment to keep suppressing pathogenic IgGs.

Results from the phase 1 study in healthy participants, phase 2 studies of participants with MG, ITP, and pemphigus, and PK/PD modeling analysis indicate that a dose of 10 mg/kg efgartigimod, administered weekly (q7d) through IV infusion achieved close to maximal IgG reduction, resulted in a reduction of pathogenic autoantibodies, and was associated with clinical efficacy in in participants with MG, ITP, and pemphigus. Furthermore, this dose was considered safe and well-tolerated in all populations. The PK and PD profile of efgartigimod appeared to be similar in all investigated populations so far. Therefore, a flat SC dose resulting in a similar PD effect as achieved with 10 mg/kg weekly IV administration is targeted as a maintenance dose for patients with pemphigus.

PK and PD data from ARGX-113-1901 (which investigated different efgartigimod PH20 SC doses) were used for a population PK/PD analysis to find an efgartigimod PH20 SC dose that results in a similar PD effect compared to efgartigimod 10 mg/kg IV. Simulations were performed to include parameter uncertainty. Outcome measures investigating comparable effects on IgG levels as the 10 mg/kg IV dosed weekly, include area under the effect-time curve days 22 to 29, maximal IgG reduction between day 22 and 29, and trough IgG reduction at day 29.

To maximize the probability of clinical improvement, both the median values and the 90% confidence interval (CI) ranges of the PD outcome parameters were considered in the dose selection. A SC dose was selected for which the predicted median value on each of the 3 outcome parameters has at least reached the median value of the IV dosing, and for which the lower limits of the 90% CI are predicted to fall within the lower limits of the IgG reduction of 10 mg/kg IV dosing. A dose of 1000 mg efgartigimod PH20 SC meets all these requirements.

Based on these simulations, a weekly dose of 1000 mg efgartigimod PH20 SC is selected as the maintenance dose for this trial. The predicted IgG reduction with weekly 1000 mg efgartigimod PH20 SC doses is comparable to that of 10 mg/kg IV efgartigimod.

As pemphigus is a chronic disease, current therapies require chronic administration. In this trial, efgartigimod with rHuPH20 will be administered via the SC route in a flat dose in a new highly concentrated formulation, which may be more convenient for patients with pemphigus.

In order to allow for a convenient SC administration with efgartigimod to achieve the targeted exposure and PD effect, efgartigimod will be coformulated with rHuPH20. This compound is being used in co-formulations with approved therapeutic antibodies to facilitate SC injection with volumes larger than 2 mL. The use of rHuPH20 in combination with other therapeutic proteins typically increases the absorption rate of these proteins, albeit to different extents. Increased rate of absorption of efgartigimod by rHuPH20 is expected to increase the overall exposure to efgartigimod after SC administration allowing administration of a SC dose in an acceptable volume and duration of administration that targets an exposure that results in a close to the maximal PD effect.

A mg efgartigimod to be administered as SC injections coformulated with rHuPH20 has been selected for this trial. This dose is anticipated to achieve close to maximal IgG reduction within sectors as achieved by 1000 mg SC at steady state.

4.4. End of Study Definition

The end of the study is defined as the date of the last visit of the last participant in the study.

A participant is considered to have completed the study if he/she has completed all periods of the study including the EoT/ET visit and any follow-up visits (if applicable).

5. TRIAL POPULATION

Protocol deviations to recruitment and enrollment criteria, also known as protocol waivers or exemptions, are not permitted. Participants who do not meet all the inclusion criteria or who have any of the exclusion criteria will not be eligible to receive any study medication.

The criteria for screening and enrollment are to be followed explicitly. If it is noted that a participant who does not meet 1 or more of the inclusion criteria and/or meets 1 or more of the exclusion criteria was inadvertently enrolled and dosed, the sponsor's designated contract research organization (CRO) medical monitor and the sponsor's medical director must be contacted immediately. The decision to discontinue a participant from the trial will be taken on a case-by-case basis, where safety and benefit/risk assessment will be considered.

5.1. Inclusion Criteria

Participants are eligible to be included in the trial only if all of the following criteria apply:

- 1. Ability to understand the requirements of the trial, to provide written informed consent (including consent for the use and disclosure of research-related health information), willingness and ability to comply with the trial protocol procedures (including required trial visits).
- 2. The participant participated in ARGX-113-1904 and completed the study or has the defined criteria for rollover.
- 3A. Contraceptive use by men and women should be consistent with local regulations regarding the methods of contraception for those participating in clinical trials and:
 - i. Male participants:
 - Male participants must agree to use an acceptable method of contraception (as described in Section 10.4.2.2) from signing the informed consent form (ICF) until the last dose of the study drug.
 - ii. Female participants:
 - Women of childbearing potential (WOCBP as defined in Section 10.4.1) must:
 - have a negative urine pregnancy test at baseline before the IMP can be administered
 - agree to use a highly effective or acceptable contraception method (as described in Section 10.4.2.1), which should be maintained at minimum until after the last dose of IMP

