- ^b In case of suspected new lesions as reported by the participants, AEs, flare, or other safety reasons, participants should come to the clinic. This may require an unscheduled visit. Depending on the reason for the visit, different assessments need to be performed. Refer to Section 8 for more information. Participants with new lesions or flare after achieving CR should return to weekly on-site visits. Participants with flare who had achieved CRmin or CRoff should switch to the visit schedule outlined in Table 2.
- ^c Follow-up 1 will be the EoS visit for participants who ended treatment before W49 or 4 weeks before ET. Both follow-up visits will be required only for participants who continue to receive efgartigimod PH20 SC for at least 1 visit between W49 and W52 or during the last 4 weeks before ET.

^d Study visit windows are ± 2 days during the treatment period and ± 3 days for the follow-up visits.

^e Weight will be measured and BMI will be calculated accordingly, at the rollover visit, at W26 (or the next on-site visit if W26 does not coincide with an on-site visit) and W52. Weight will also be measured if there has been an obvious change since the last measurement.

^f Assessment or procedure will be completed predose at visits when IMP is administered.

^g The ECG will be recorded at baseline, every 3 months while receiving efgartigimod PH20 SC treatment, at CRmin (or the next on-site visit if CRmin is achieved during a week without an on-site visit), and at EoS. The ECG (heart rate, PR, QT, and QRS interval) will be read centrally, and QTcF and QTcB will be calculated. The ECG will be recorded only at baseline and EoS in participants not receiving efgartigimod. Additional ECGs may be performed at the discretion of the investigator during unscheduled visits.

- ^h A complete physical examination will be performed at each on-site visit. Vital sign measurements include systolic and diastolic blood pressure, heart rate, and body temperature.
- ⁱ Urinalysis will be performed by dipstick method and will include specific gravity, pH, protein, glucose, ketones, blood, bilirubin, urobilinogen, nitrite, leukocyte esterase, and microscopic examination (if blood or protein is abnormal).
- ^j A urine pregnancy test will be performed locally and at least once every 4 weeks.

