- ^t Efgartigimod PH20 SC will be administered weekly at a dose of 1000 mg until CRmin. For IMP administrations between the scheduled site visits, the participant can choose between self-administration (if training successfully completed), home nurse visits, or return to the trial site for the SC injection only. Participants who have achieved CRmin or CRoff and are currently not in flare will be observed every 4 weeks without any further IMP administration until flare or EoS. Only for on-site visits and home nurse visits, participants should be followed up for safety monitoring for at least 1 hour after the first IMP administration, or followed by 15 minutes of observation for subsequent administrations and released according to their clinical status. The last planned IMP administration is at W52. If the participant withdraws from the study, efgartigimod PH20 SC will not be administered.
- ^u Prednisone dose tapering will begin 2 weeks after achieving CR or 4 weeks after sustained EoC (thus, no new lesions have developed for a minimum of 6 weeks and approximately 80% or more of lesions have healed).

Table 2:Schedule of Activities for ARGX-113-1905 for Participants Not in CR at Rollover From ARGX-113-1904, or
Participants With Flare after CRmin or CRoff in ARGX-113-1905

Trial period	V1 ^a	Observational visits	IMP admin only visit	Observati	EoT/ET		Follow-up		
Visit Number		Weekly on-site visits until CR ^b	Weekly home or on-site visits until CRmin ^c	On-site visits every 4 weeks until CRmin	On-site visits every 4 weeks until W52	W52		Safety follow-up 1	Safety follow-up 2
Trial Week	Rollover ^a	V1 + 7x	CR until CRmin	CR until CRmin	After CRmin until W52	W52	UNS ^d	EoT/ET + 4 weeks ^e	EoT/ET + 8 weeks EoS ^e
Assessment/Procedure	±0 days		±2	days ^f		±2 days		±3 (lays ^f
Informed consent	Х								
Inclusion/exclusion criteria	X								
Weight ^g	Х	X ^g		X ^g	X ^g	Х			
ECG ^{h,i}	X	Х		Х	Х	X		Х	Х
Physical examination and vital signs ^{i,j}	X	Х		Х	X	Х	X	X	Х
Urinalysis ^{i,k,l}	X	Х		Х	Х	X	X ^d	Х	Х
Urine pregnancy test ^{i,m}	Х	Х		Х	Х	X	X ^d	X	Х
Vaccination antibodies ^{i,1}	Х	X		Х	Х	X	X ^d	X	X
Blood sampling									
 Clinical chemistry and hematology^{i,l,n} 	X	Х		Х	X	Х	Xd	Х	Х
 anti-Dsg-1 and anti- Dsg-3 antibodies^{i,1} 	X	X		X	X	X	X ^d	Х	Х

Trial period									
	V1 ^a	Observational visits	IMP admin only visit	Observati	EoT/ET		Follow-up		

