ABQOL=Autoimmune Bullous Disease Quality of Life; AE=adverse event; ALT=alanine aminotransferase; ALP=alkaline phosphatase; AST=aspartate aminotransferase; BMI=body mass index; BUN=blood urea nitrogen; CR=complete clinical remission; CRmin=CR on minimal therapy; CRP=C-reactive protein; DC=disease control; Dsg=desmoglein; ECG=electrocardiogram; EoC=end of consolidation; EoS=end of study; EoT=end of treatment; EQ-5D-5L=EuroQol 5-dimension 5-level scale; ET=early termination; GGT=gamma-glutamyl transferase; GTI=Glucocorticoid Toxicity Index; IgG=immunoglobulin type G; IMP=investigational medicinal product; LDH=lactate dehydrogenase; MCV=mean corpuscular volume; NAb=neutralizing antibody; PD=pharmacodynamic; PDAI=Pemphigus Disease Area Index; PK=pharmacokinetics; QTcF=Fridericia corrected QT interval; rHuPH20=recombinant human hyaluronidase PH20; RBC=red blood cells; SC=subcutaneous(ly); UNS=unscheduled visit; V=visit at site; V1 + 7x=visit 1 + 7 times x with 'x' being the weeks post V1 (eg, V1 + 7x3 is the visit at W3 [21 days post visit 1]); W=week; WBC=white blood cells

^a For participants who roll over from ARGX-113-1904 to ARGX-113-1905, the baseline visit will occur at the EoS/ED visit of ARGX-113-1904. All assessments are performed before IMP administration.

^b A minimum of 6 on-site visits (rollover (V1) to W6 or start of retreatment +5 weeks) is required before switching to home administrations, even if CR is reported earlier.

^c Home visits are allowed once a participant achieves CR but not before W7 or not before the start of retreatment +6 weeks. The investigator should call the participant every 2 weeks until CRmin to confirm the participant is still in CR and to determine the prednisone tapering schedule.

^d In case of suspected new lesions as reported by the participant, AEs, flare, or other safety reasons, the participant should come to the clinic. This may require an unscheduled visit. Depending on the reason for the visit, different assessments need to be performed. Refer to Section 8 for more information.

^e Follow-up 1 will be the EoS visit for participants who ended treatment before W49, or 4 weeks before ET. Both follow-up visits will be required only for participants who continue to receive efgartigimod PH20 SC for at least 1 visit between W49 and W52, or during the last 4 weeks before ET.

^f Study visit windows are ± 2 days during the treatment period and ± 3 days for the follow-up visits.

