- RMI will be calculated accordingly, at the follover visit, at W26 (or the next on-site visit if W26 does not coincide with an on-site
- ^g Weight will be measured and BMI will be calculated accordingly, at the rollover visit, at W26 (or the next on-site visit if W26 does not coincide with an on-site visit) and W52. Weight will also be measured if there has been an obvious change since the last measurement.
- ^h The ECG will be recorded at baseline, at the start of retreatment and every 3 months (or the next on-site visit) while receiving efgartigimod PH20 SC treatment, at CRmin (or the next on-site visit if CRmin is achieved during a week without an on-site visit), and EoS. The ECG (heart rate, PR, QT, and QRS interval) will be read centrally, and QTcF and QTcB will be calculated. Additional ECGs may be performed at the discretion of the investigator during unscheduled visits.
- ⁱ Assessment or procedure will be completed predose at visits when IMP is administered.
- ^j A complete physical examination will be performed at each on-site visit. Vital sign measurements include systolic and diastolic blood pressure, heart rate, and body temperature.
- ^k Urinalysis will be performed by dipstick method and will include specific gravity, pH, protein, glucose, ketones, blood, bilirubin, urobilinogen, nitrite, leukocyte esterase, and microscopic examination (if blood or protein is abnormal).
- ¹ Samples will be taken every week from rollover (V1) to W9 or start of retreatment +8 weeks, and then every 4 weeks and at the visit when CR is observed. Once CR is achieved, samples will be taken every 4 weeks at on-site visits until EoS. For participants achieving CR between rollover (V1) and W6 or the start of retreatment +5 weeks, samples will be taken weekly from rollover (V1) to W6 or start of retreatment +5 weeks, and then every 4 weeks during on-site visits until EoS.
- ^m A urine pregnancy test will be performed locally at least once every 4 weeks, at CR, and as of CR again every 4 weeks at on-site visits.
- ⁿ Clinical blood laboratory tests will include hematology and blood chemistry at all visits. The hematology profile includes hemoglobin, hematocrit, MCV, RBC count, platelet count, WBC count with differential. The blood chemistry profile includes sodium, potassium, calcium, HbA1c, creatinine, creatinine clearance, BUN, ALT, AST, total bilirubin, GGT, CRP, ALP, LDH, low-density lipoprotein cholesterol (LDL-C), uric acid, total protein, and albumin.

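### No text requires a negative pregnancy test before the first dose of a retreatment cycle, and the Table 5 dosing cell for flare visits leaves that dose out

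*Protocol*

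**What the plan says.** The only express rule linking a negative test to dosing is criterion 3A.ii: "have a negative urine pregnancy test at baseline before the IMP can be administered". Section 4.1 sets the baseline visit on the same date as the end-of-study or early-discontinuation visit of ARGX-113-1904.

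Participants in CRmin or CRoff who are "currently not in flare will be observed every 4 weeks without any further IMP administration until flare or EoS" (Table 1, footnote t). If they flare, Section 4.1 says "participants will be immediately treated/retreated with a new cycle of efgartigimod PH20 SC". The first day of that cycle "will define a new baseline for assessments of outcomes (DC, CR, etc) and prednisone escalation or tapering schedule".

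On testing frequency, Table 1 footnote j says "A urine pregnancy test will be performed locally and at least once every 4 weeks". Table 2, which governs retreatment, says in footnote m "A urine pregnancy test will be performed locally at least once every 4 weeks, at CR", and then 4-weekly again from CR onward.

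The pregnancy-test marks in the unscheduled-visit columns of both tables carry a footnote: "Depending on the reason for the visit, different assessments need to be performed. Refer to Section 8 for more information". In Section 8, Table 5 marks the urine pregnancy test for unscheduled visits made for other reasons and leaves the new-lesion and flare columns blank. For study drug, the Table 5 flare cell permits dosing only when the visit falls on a planned drug-administration visit.

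**The concern.** Section 2.3.1 states that efgartigimod should not be given in pregnancy, and 3A.ii enforces this at entry with a negative test. Starting a new course after weeks or months off drug is a comparable moment, but the safeguard is not written there. For a participant who rolled over already in CRmin or CRoff, the retreatment dose is the first study drug in this trial. If she had been on placebo in ARGX-113-1904, it is her first efgartigimod. Section 4.1 allows new cycles up to week 44, and optionally up to week 49, so the 3A.ii test may be that old, with only the 4-weekly schedule in between.

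The second problem is a conflicting instruction. For a participant off drug, the Table 5 dosing cell cannot be met, while Sections 4.1 and 8 order immediate retreatment. What is at stake is avoidable fetal exposure in a small number of women and an unclear site instruction. No analysis depends on it.

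**Working it through.** There is no planned figure to reproduce. The check sets the texts side by side and then counts days.

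**Does any text make a negative test a condition of the first retreatment dose?**

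| Source | What it provides | Covers the retreatment start? |
|---|---|---|
| 3A.ii (Section 5.1) | Negative test before drug at baseline | No; baseline is roll-over |
| New baseline (Sections 4.1 and 8) | Resets outcomes and the prednisone schedule | No; dosing eligibility is not named |
| Table 2, V1 column | Test marked | No; the column is labelled roll-over |
| Table 2, weekly on-site column | Test marked, qualified by footnote m | Not expressly; m sets a 4-weekly minimum plus CR |
| Table 2, footnote i | Due assessments are done before dosing | Sets order only; neither makes a test due nor requires a negative result |
| Table 2, footnotes h, l and s | ECG, urinalysis and blood samples, questionnaires | These name the start of retreatment; footnote m does not |
| Table 5, flare column | Pregnancy test blank | No |
| Sections 7.2, 8.4.6 and 10.4.3.2 | Action once a pregnancy is known | No test attached |

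**Age of the last required test at redosing.** Take required tests on days 0 and 28, and an unscheduled flare visit on day d between them.
- Without windows, d runs from 1 to 27, so the maximum age is 27 days. If visits fall evenly over those days (assumption), the mean is (1 + 27)/2 = 14 days.
- With the ±2-day windows, the interval can reach 28 + 2 + 2 = 32 days. The maximum age is then 31 days and the mean (1 + 31)/2 = 16 days.
- Section 8 brings participants with new lesions in CRmin or CRoff back weekly. If those visits line up with the 4-weekly ones (assumption), 3 of every 4 are unscheduled, with a last required test 7, 14 or 21 days old.
- A flare confirmed at a planned 4-weekly visit has a same-day test, so the age is 0.

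**Weekly doses before the next required predose test**, for interval L and redosing on day d: floor((L − 1 − d)/7) + 1.
- L = 28: 4 doses for d = 1–6 (6 days), 3 for d = 7–13 (7 days), 2 for d = 14–20 (7 days), 1 for d = 21–27 (7 days). The sum is 24 + 21 + 14 + 7 = 66, and the mean is 66/27 = 2.44.
- L = 32: 5 doses for d = 1–3, 4 for d = 4–10, 3 for d = 11–17, 2 for d = 18–24, 1 for d = 25–31. The sum is 15 + 28 + 21 + 14 + 7 = 85, and the mean is 85/31 = 2.74.

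**The Table 5 dosing cell.** Between DC and CRmin, weekly dosing continues, so a flare visit can coincide with a planned dose and the cell works. After CRmin or CRoff no dose is planned, so read literally the cell never permits the first dose of the new cycle. The Section 8 text above the table and the efgartigimod mark in the unscheduled columns of Tables 1 and 2 point the other way.

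**The case against.** The strongest reply is that Table 2 already covers this visit. It is the schedule for participants who flare after CRmin or CRoff, its pregnancy row is marked in both the V1 and weekly columns, and footnote i puts due assessments before dosing. Footnote b says "A minimum of 6 on-site visits (rollover (V1) to W6 or start of retreatment +5 weeks) is required before switching to home administrations", which treats the retreatment start as parallel to roll-over. A 4-weekly minimum does not forbid more frequent testing, and Section 8 adds the assessments of any coinciding planned visit to those in Table 5. A careful site may well test on the day, and then the gap is zero. That stands as a plausible reading, but it is not an express requirement: V1 is labelled roll-over, footnote m omits retreatment where neighbouring footnotes name it, and nothing makes a negative result a condition of that dose.

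It is also fair that dosing in pregnancy is already barred, contraception is required, and weekly-treated women are likewise tested only 4-weekly. The cited animal studies showed no teratogenic effect. Section 2.2 puts peak disease frequency at ages 50 to 60, so few women may be affected. All of this limits the severity. It does not supply the missing condition, which the protocol itself judged necessary before the first dose at entry.

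The dosing-cell conflict is unlikely to stop a site from retreating, because other text overrides it in part. It remains a contradictory instruction.

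**Conclusion.** The concern holds as a minor safety clarification. For a flare off drug confirmed at an unscheduled visit, no text expressly requires a negative test before the new cycle, and Table 5 omits both the test and the first dose. If the site does not test on the day, the last required test is 1 to 27 days old (up to 31 with windows). A pregnancy detectable but untested at redosing would receive 1 to 4 weekly doses, mean 2.4, before the next required test; at the 32-day interval this is 1 to 5, mean 2.7. The means assume that unscheduled flare visits are spread evenly between 4-weekly visits. The documents do not say how many women of childbearing potential would be retreated, so the expected number of exposures cannot be given. No endpoint, analysis set or SAP derivation is affected.

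**What to change.** Four wording changes:
- In footnote m of Tables 2 and 9, add: *and at the start of each retreatment cycle, with a negative result before the first dose*.
- Add the same condition to criterion 3A.ii.
- In Table 5, mark the urine pregnancy test in the flare column when a new cycle starts.
- In the Table 5 dosing cell for flare, add: *or as the first dose of a new cycle once flare after CRmin/CRoff is confirmed*.

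The cost is protocol wording and one local urine dipstick per retreatment start. No extra visit is needed. Retreatment begins on site (Table 2 footnote b; Appendix 11 requires this even under pandemic rules), and footnote l already calls for weekly urine samples for urinalysis from that day. With the change, the age of the last test at redosing is 0 days.
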